7.1.3 Mode of action

- **Lupron** possesses greater potency than the natural hormone. Leuprolide acetate, a LHRH agonist, acts as a potent inhibitor of gonadotropin secretion when given continuously and in therapeutic doses. Human studies indicate that following an initial stimulation, chronic administration of leuprolide acetate results in suppression of ovarian and testicular steroidogenesis. This effect is reversible upon discontinuation of drug therapy. Administration of leuprolide acetate has resulted in inhibition of the growth of certain hormone dependent tumors (prostatic tumors in Noble and Dunning male rats and DMBA-induced mammary tumors in female rats) as well as atrophy of the reproductive organs. In humans, administration of leuprolide acetate results in an initial increase in circulating levels of luteinizing hormone (LH) and follicle stimulating hormone (FSH), leading to a transient increase in levels of the gonadal steroids (testosterone and dihydrotestosterone in males, and estrone and estradiol in premenopausal females). However, continuous administration of leuprolide acetate results in decreased levels of LH and FSH. In males, testosterone is reduced to castrate levels. These decreases occur within two to four weeks after initiation of treatment, and castrate levels of testosterone in prostatic cancer patients have been demonstrated for more than five years with continuous drug administration.
- **Zoladex** is a LHRH analog with substitutions for the L-amino acid Glycine in positions 6 and 10. These substitutions produce analog with 50-100 times the potency and longer duration of action than the naturally occurring peptide when assessed in acute animal tests.

- **Casodex** is a racemic mixture with the anti-androgen activity residing exclusively in the (-) or (R) enantiomer.
- **Eulexin** Flutamide is a non-steroid anti-androgen that is metabolized into a hydroxylated derivative, which effectively competes with the hydrotestosterone for androgen receptor sites.

7.1.4 Storage and stability

The agents are commercially available and received in manufacturer's packaging. If administered through syringe, the drugs are in sterile units and come in a sealed, light- and moisture-proof package. The packs should be stored at approximately 25° C (room temperature). Before being opened, each package must be inspected for damage in which case the syringe must not be used. The drugs that are administered orally also come in packs, which should be stored at room temperatures and protected from excessive moisture. Since the drugs are part of the routine treatment of prostate cancer they will be handled by the treating physician according to the manufacturer specifications.

7.1.5. Dose specifics

- **Lupron** is recommended as 7.5 mg (*one month*), 22.5 mg (*three month*) or 30 mg (*four month*) intramuscular depot injections in the combinations described above to achieve a total duration of 4-6 months.
- **Zoladex** is recommended as 3.8 mg (*one month*) or 10.8 mg (*three month*) depot subcutaneous injections in the combinations described above to achieve a total duration of 4-6 months.
- **Casodex** 50 mg has the status of an approved new drug. Casodex has a long half-life compatible with once-daily dosing. Anti-androgen will be given for a maximum of four months.
- **Eulexin** is supplied as 125 mg capsules and is commercially available. Anti-androgen will be given for a maximum of four months.

7.1.6 Preparation

The agents are commercially available and no preparation is required.

7.1.7 Administration

The injectable agents will be administered by the study urologists in their offices, as part of routine clinical practice. The oral agents will be prescribed by the treating physician as part of routine clinical practice.

- **Lupron** is administered by intramuscular injection. Each kit contains a vial of sterile lyophilized microspheres, which is leuprolide incorporated in a biodegradable polymer of polylactic acid. Any formulation may be used. Product does not contain preservative and should be discarded if not used immediately.
- **Zoladex** 10.8-mg depot is supplied with a 14-gauge needle. Being sterile, the syringe should be removed from its package only by the physician/nurse immediately before use. Zoladex will be injected subcutaneously using an aseptic technique. The needle should be inserted to its full length, pulled back 1cm and then injected. The manufacturer recommends inserting the needle into the subcutaneous fat then changing the direction of the needle so that it parallels the abdominal wall before inserting the needle to its full length. This will create a little pocket for the Zoladex plug so that it does not extend when the needle is withdrawn. After rechecking to ensure that the depot has been discharged, the used syringe will be discarded in a safe manner. One can ensure that the depot has been discharged by ensuring the tip of the plunger is visible within the tip of the needle.

- **Casodex** is administered orally at a dose of one 50 mg tablet per day. Casodex will be started from two weeks to one day prior to LHRH administration and continued throughout radiotherapy. Administration will be suspended only if there is an apparent or suspected reaction to the drug. Bicalutamide will be terminated on the last day of radiotherapy. During radiotherapy interruptions, Casodex will be continued.

- **Eulexin** is administered orally at a dose of two 125 mg capsules three times a day for a total daily dose of 750 mg (six capsules).

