4.15 Duration of Therapy

- Within 4 weeks of enrollment, patients will be biopsied (patient may refuse) and fiducial markers placed.
- LHRH agonist androgen deprivation therapy: LHRH agonist therapy may start up to two months prior to signing consent form or any time after signing consent form, up to two weeks after fiducial marker placement (preferred) in men with intermediate or high (optional) risk prostate cancer. All patients may receive 4-6 months (+/- 2 months) LHRH agonist therapy.
- Anti-androgen treatment should begin 1-14 days prior to LHRH agonist injections. Anti-androgen will be continued four 4 months.
- .
- Standard fraction RT: Day 2 of radiotherapy will start within 32 hr of LEAD RT and will consist of 38 fractions at 2.0 Gy over 7.5 weeks
- Treatment will be stopped for grade 4 acute toxicity (according to the current version of Common Terminology Criteria for Adverse Events (CTCAE version 4), but may be resumed per protocol if the treatment break is less than 10 working days. Since we have never observed grade 4 toxicity acutely using IMRT (conformal CyberKnife treatment is an IMRT-like treatment),

such an event is unlikely. If grade 4 toxicity resolves beyond the 10 days the treating physician will decide whether to give additional RT.

- Treatment will be stopped if metastasis is detected by radiographic or pathologic evidence and the patient will be removed from the study, but not from intent-to-treat analysis. A work-up for metastasis during treatment will only be carried out if the treating physician deems necessary.
- Multiparametric MRI exams of the prostate/pelvis will be carried out after RT at 3 months, 9 months, and within 2 months of the post-treatment prostate biopsies.
- Prostate biopsies will be taken at 2-2.5 years post completion of all therapy.

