6.2 Other Agent(s)

Lupron (leuprolide acetate), Zoladex (goserelin), Casodex (bicalutamide) and Eulexin (flutamide) or other equivalent generic agents are used in routine management of prostate cancer for androgen deprivation. These drugs are not study specific and are standard for prostate cancer; they will not be supplied by the pharmacy at SCCC.

Short term androgen deprivation (STAD) for 4-6 months (+/- 2 months) may be administered to some patients as described in sections 3.1 and 4.7. This timing is based on LHRH agonist injections (not the bicalutamide).

STAD will consist of oral antiandrogen administration and LHRH agonist injections to begin within the aforementioned timeframe. The antiandrogen will be either flutamide at 250 mg p.o. TID or bicalutamide at 50 mg p.o. QD. Antiandrogen therapy should begin at approximately the same time as LHRH agonist injection but may be started up to two weeks earlier. Antiandrogen administration will be given for up to four months. The length of STAD therapy will be pegged to the anticipated duration of LHRH agonist therapy. LHRH agonist injections (Lupron or Zoladex) may be given in any possible combination, such that the total LHRH agonist treatment time is 4-6 months (+/- 2 months). For example, LHRH agonist injection(s) may be

given as a single 4-month injection, a 4-month injection and one to two 1-month injection(s), two 3-month injections, one to three 1-month and a 3-month injection (4-6 months total), four to six 1-month injections, or a 6-month injection.

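### For men who start ADT up to two months before consent and take bicalutamide continuously, 7.1.7 runs the drug to the end of RT, past the four-month maximum in 6.2 and 7.1.5

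*Combined protocol and SAP*

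**What the plan says.** **Stop rule.** Section 7.1.7 begins bicalutamide between two weeks and one day before the LHRH agonist and keeps it going through RT. A suspected drug reaction is the only ground for suspension. It then says "Bicalutamide will be terminated on the last day of radiotherapy" and "During radiotherapy interruptions, Casodex will be continued".

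**Cap.** Section 6.2 says "Antiandrogen administration will be given for up to four months". Section 7.1.5 says "Anti-androgen will be given for a maximum of four months". Section 4.15, as printed, says "Anti-androgen will be continued four 4 months", which reads as a fixed length rather than a limit. No section says which rule governs if they collide.

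**Timing.** Section 6.2: "Antiandrogen therapy should begin at approximately the same time as LHRH agonist injection but may be started up to two weeks earlier". Section 4.15: "LHRH agonist therapy may start up to two months prior to signing consent form or any time after signing consent form", with a start around fiducial placement preferred. Also in 4.15: "Within 4 weeks of enrollment, patients will be biopsied (patient may refuse) and fiducial markers placed". Section 4.6 puts the simulation MRI at least a week after the fiducials. LEAD is given on a Monday, Tuesday or Wednesday (4.8), followed by 38 fractions over 7.5 weeks (4.15).

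**Liver tests.** Section 7.1.8 requires AST or ALT before treatment and every other month on either anti-androgen, with a mandatory stop at twice the upper limit of normal. Sections 5.1 to 5.3 and Appendix I schedule liver function tests at baseline, in the last RT week, and at 6 weeks and 3 months after RT.

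**The concern.** One section fixes the end of bicalutamide by an event (the last RT day) and two others fix it by a duration (four months). The two agree only if the first dose comes late enough. The protocol expressly permits an LHRH start well before consent, and consent is followed by fiducial placement, a week's wait and about seven and a half weeks of RT. If those intervals add up to more than four months, a permitted patient cannot be treated without breaking one instruction. Following 7.1.7 exceeds a stated maximum for a drug with its own liver-toxicity stopping rule. Stopping at four months breaks the instruction to continue through RT. Staff have no text to tell them which to do, and patients in the same position could be handled differently.

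**Working it through.** **Reproducing the RT length.** Count 38 weekday fractions starting the day after LEAD. The last fraction falls 52 days after a Monday or Tuesday LEAD and 54 days after a Wednesday LEAD. First to last fraction inclusive is 52 to 54 days, or 7.4 to 7.7 weeks, in line with the stated 7.5.

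**Cap in days.** With 30.44 days per month, 4 × 30.44 = 121.75, about 122 days.

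**Formula.** Exposure = lead-in before LHRH + LHRH start to consent + consent to fiducials + fiducials to simulation + planning + LEAD to last fraction.

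Inputs:
- Lead-in: 1 to 14 days (7.1.7), or 0 with the same-day start in 6.2.
- LHRH start to consent: up to 61 days (4.15).
- Consent to fiducials: 0 to 28 days (4.15), taking enrollment as the day of consent.
- Fiducials to simulation: at least 7 days (4.6).
- Planning, simulation to LEAD: not stated. Set to 0, which favors compliance.
- LEAD to last fraction: 52 to 54 days.

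| LHRH start | Shortest (days) | Longest (days) | Against about 122 |
|---|---|---|---|
| Two months before consent | 1 + 61 + 0 + 7 + 0 + 52 = 121 (120 with same-day start) | 14 + 61 + 28 + 7 + 0 + 54 = 164 | over, except near the minimum |
| One month before consent | 1 + 30 + 0 + 7 + 0 + 52 = 90 | 14 + 30 + 28 + 7 + 0 + 54 = 133 | over only with slow scheduling |
| Day of consent | 1 + 0 + 0 + 7 + 0 + 52 = 60 | 14 + 0 + 28 + 7 + 0 + 54 = 103 | under |
| At fiducial placement | 0 + 7 + 0 + 52 = 59 | 14 + 7 + 0 + 54 = 75 | under |

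For the two-month start, the largest excess is 164 − 122 = 42 days. The 121-day path needs fiducials on the day of consent, LEAD on the day of simulation, a one-day lead-in and a Monday or Tuesday LEAD. Moving LEAD to Wednesday gives 1 + 61 + 0 + 7 + 0 + 54 = 123 days, already over.

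**General threshold.** The two rules collide when the first dose is more than 121.75 − 54 = 67.75 to 121.75 − 52 = 69.75 days before LEAD, about 68 to 70 days.

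**Planning time.** If 0 to 14 days is assumed, the longest two-month path becomes 164 + 14 = 178 days. The consent-day path (103 + 14 = 117) and the fiducial-day path (75 + 14 = 89) stay under. RT interruptions also add to exposure, because 7.1.7 continues the drug through them.

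**Liver tests for early starters.** The last RT week is taken as up to 6 days before the final fraction. From a baseline drawn on the day of consent, the next scheduled test is 0 + 7 + 46 = 53 to 28 + 7 + 54 = 89 days later. If the baseline preceded the first dose, the next scheduled test is 0 + 61 + 53 = 114 to 14 + 61 + 89 = 164 days after that dose. Section 7.1.8 asks for a test about every 61 days.

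**The case against.** ADT is optional here, the drugs are described as standard care, and the recommended start after fiducial placement causes no conflict. For an early starter, up to 14 + 61 = 75 days of bicalutamide come before consent, when the protocol does not yet direct prescribing. Section 7.1.10 recommends an anti-androgen only for the first month of LHRH treatment, so a man might arrive having already stopped. The protocol also does not say whether pre-consent doses count toward the four months. All of this stands. It limits the point to men who take the drug continuously from an early start, and it is why the fix must say how pre-consent doses are counted. It does not remove the conflict: the protocol admits these men, prescribes the drug's duration, and names a reaction as the only ground for suspension, so the cap cannot be read in as an implied exception.

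A reader might infer that the liver-test schedule contradicts 7.1.8 or leaves early starters without required monitoring. The documents do not support that. Section 7.1.8 is binding on its own, and nothing makes Appendix I exhaustive. For a two-month-early starter, a baseline drawn at consent falls about two months into treatment and can serve as the first on-drug check. What remains is a calendar that does not prompt a test already ordered.

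Giving the cap priority is also a clinical choice: the sponsor could instead extend the cap for early starters. That stands, and the fix states it.

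**Conclusion.** The inconsistency is real and narrow. With LHRH at the two-month limit, the two rules cannot both be followed on all but a near zero-delay path. The result rests on uninterrupted bicalutamide from the early start, pre-consent doses counting toward the maximum, enrollment on the day of consent, and no planning time. The documents do not give the number of patients affected.

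Wider readings are not supported. Bicalutamide patients in general are not affected, since a start at fiducial placement complies. Flutamide has no RT-end stop in 7.1.7 and is outside the duration conflict. ADT length does not change, because 6.2 times it by the LHRH agonist. The toxicity stopping rule in 14.4 counts GI and GU events, and its boundaries, the feasibility rule and every statistical figure are untouched.

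**What to change.** - **7.1.7:** state that bicalutamide ends on the final RT day or four months after its first dose (pre-consent doses included), whichever is earlier, and sooner if AST or ALT reaches twice the upper limit of normal or a reaction is suspected.
- **4.15:** change the anti-androgen duration to *for up to four months*.
- **5.2 and Appendix I (secondary, for consistency):** add AST/ALT every two months while an anti-androgen is being taken, as 7.1.8 already requires.

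The cost is one sentence, one phrase and one calendar line, with no new test. The downside is that some early starters will stop bicalutamide during RT while the LHRH agonist continues on its own schedule. On the 164-day path, LEAD falls 14 + 61 + 28 + 7 = 110 days after the first dose, so the cap is reached about 122 − 110 = 12 days into RT. More than about 12 days of planning on that path would bring the stop before LEAD. The first-month recommendation in 7.1.10 is still met. If the sponsor wants bicalutamide through RT for these men, it should instead write that exception into the cap in 6.2 and 7.1.5.

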7.1.8 Incompatibilities/Dose Modification

- **Casodex** should be discontinued in instances of chemical liver toxicity. AST or ALT will be measured pretreatment and then every other month during anti-androgen therapy. If the AST or ALT rises $\geq 2x$ the institutional upper limit of normal, **Casodex** must be discontinued. If liver enzymes are rising and of concern to the treating physician, Casodex may be discontinued earlier.

- **Eulexin**: If gastrointestinal disturbances (cramps, diarrhea) occur prior to initiation of radiotherapy, the drug will be withheld until the side effects subside; the drug will then be reintroduced at a dose of 250 mg/day and increased (at 3-day intervals) to 500 mg/day and then to 750 mg/day as tolerated. If gastrointestinal disturbances occur after administration of radiotherapy, it might be difficult to identify their cause. However, if severity of diarrhea exceeds the level commonly observed during pelvic irradiation, the toxicity will be ascribed to Eulexin and the drug will be permanently discontinued. AST or ALT will be measured pretreatment, then about every other month during oral anti-androgen therapy. If AST or ALT increases $\geq 2x$ the upper institutional limit of normal, flutamide must be discontinued.

7.1.9 Availability

The agents are commercially available and will not be dispensed by the Sylvester pharmacy.

7.1.10 Side effects

- **Lupron**: In the majority of patients testosterone levels increased above baseline during the first week, declining thereafter to baseline levels or below by the end of the second week of treatment. The most common side effect of Leuprolide is vasomotor hot flashes; edema, gynecomastia, bone pain, thrombosis, and GI disturbances have occurred. Potential exacerbations of signs and symptoms during the first few weeks of treatment is a concern in patients with vertebral metastases and/or urinary obstruction or hematuria which, if aggravated, may lead to neurological problems such as temporary weakness and/or paresthesia of the lower limbs or worsening of urinary symptoms

- **Zoladex**: During routine screening of Zoladex, no significant pharmacological activity was apparent in the cardiovascular, respiratory, central nervous, renal, metabolic, coagulation or gastric acid secretory systems. Studies have shown that serum levels of testosterone can be reduced and maintained within the castrate range resulting in objective evidence of tumor regression. Other than the occasional transient worsening of cancer symptoms (tumor flare) due to an initial temporary rise in testosterone serum levels on initiating therapy, no significant toxicity apart from that attributed to castration (hot flashes, decreased erections, impotence) has been reported. In general, allergic reactions have been extremely uncommon with Zoladex therapy. There have been isolated reports of urethral obstruction, urticaria, or spinal cord compression.

- **Casodex**: The drug is well tolerated and has good response rates in phase II trials. Non-pharmacological adverse events, reported in the trial using bicalutamide 50 mg as

monotherapy include asthenia, pelvic pain, peripheral edema, pruritus, rash, constipation, impotence, dyspnea, nausea, and pain.⁹³ There has been no observed change in cardiac parameters during long-term administration of bicalutamide 50 mg daily. When bicalutamide 50 mg was given in combination with an LHRH analogue, the LHRH analogue adverse event profile predominated with a high incidence of hot flashes (49%) and relatively low incidences of gynecomastia (4.7%) and breast pain (3.2%), the associated pharmacological effects of bicalutamide monotherapy.⁹³ Bicalutamide or flutamide is recommended during the first month of LHRH agonist treatment.

- **Eulexin:** The reported side effects of treatment include diarrhea and anemia. A high percentage of patients treated with flutamide alone developed gynecomastia within 2-8 months. There have been post-marketing reports of hospitalization, and, rarely, death due to liver failure in patients taking flutamide. Evidence of hepatic injury included elevated serum transaminase levels, jaundice, hepatic encephalopathy, and death related to acute hepatic failure. The hepatic injury was reversible after prompt discontinuation of therapy in some patients. Approximately half of the reported cases occurred within the initial 3 months of treatment with flutamide.

7.1.11 Nursing implications

N/A

7.1.12 Reported Adverse Events and Potential Risks

N/A

8.0 CORRELATIVE/SPECIAL STUDIES

Prior to treatment during fiducial markers placement, patients who choose to have biopsies will undergo needle biopsy of the prostate. Tissue from paraffin blocks will be used for biomarker quantification and correlative studies with treatment outcome.

At 2-2.5 years after completion of treatment (radiotherapy or androgen deprivation – whichever is longer) all patients, with or without documented failure will undergo needle biopsy of the prostate, unless clinically contraindicated or the patient refuses. . A total of 12-14 biopsy cores, are preferred; although the number could be less if the physician thinks it is not appropriate to continue. Biopsies may be obtained from any suspicious functional MRI areas and/or the original site of biopsy confirmation of prostate cancer at diagnosis. These data will enable us to evaluate the extent of disease eradication, as well as the prognostic significance of positive biopsies in men who are otherwise free of evidence of disease (low PSA and palpably normal prostate gland). The Eigen Artemis® system fusion software (not FDA approved) may be used to fine-tune the location of the tumor and biopsies by fusion of the previously obtained multiparametric MRI to the transrectal ultrasound in real time. The ultrasound is the true guidance imaging parameter that identifies the prostate boundaries and other nearby structures. The MRI is fused to the ultrasound such that the biopsies may be directed to a region in the ultrasound space.

If the research biopsies contain prostate tumor cells, the results will be discussed with the patient and additional management considerations (e.g., rebiopsy) made apart from this clinical trial. Many times tumor cells are seen on prostate biopsies at 2-2.5 yr, but the cells show radiation treatment effect. In this situation, it is reasonable to continue to follow the PSA and rebiopsy a year later to look for clearance of the tumor cells. The strategy to rebiopsy will be up to the treating physician and will not be governed by the protocol.

